NCT03628872

Title: Er:YAG versus Scaling and Root Planing for the Treatment of Periodontal

Disease: A Single-Blinded Split-Mouth Randomized Clinical Trial

Protocol Version #: Laser2017v1

IRB Approved Effective Date: 01/26/2018

Protocol: AAAR6077

Protocol Status: Approved Effective Date: 01/26/2018

Expiration Date: 01/09/2019

Principal Investigator: [name]

Co-investigator and lead author: [name]

Co-investigator: [name] Co-investigator: [name]

Title: Er:YAG versus Scaling and Root Planing for the Treatment of Periodontal Disease: A

Single-Blinded Split-Mouth Randomized Clinical Trial

Protocol Version #: Laser2017v1

Abbreviated Title: Treatment of Periodontitis with Er:YAG laser

BACKGROUND

STUDY PURPOSE AND RATIONALE

The purpose of this study was to examine the changes in clinical parameters 3 months after non-surgical periodontal treatment was performed with two different treatment modalities, conventional scaling and root planing and Er:YAG laser.

STUDY DESIGN

The study was conducted as a randomized, split-mouth clinical trial. Thirty subjects were recruited and right and left side (upper and lower quadrant on each side) of the patients' mouths were randomly assigned to the two treatment modalities:

1. Conventional scaling and root planing:

Treatment was performed with Cavitron® and hand instrumentation (11/12 and 13/14 gracey's, 11/12 and 13/14 mini gracey's, 4R/4L curette and sickle scaler)

2. Er:YAG laser:

Treatment was performed with Cavitron® and the laser set at 50 mJ and 20pps, with water irrigation (set at 10) and air cooling (set at 7). C400F and PS600T tips (J. MORITA MFG. CORP, Kyoto, Japan) were used. Er:YAG was used for further calculus removal; root debridement and decontamination; ablation of the epithelial lining to avoid downgrowth of epithelium; and ablation of diseased connective tissue, in the inner surface of the gingival epithelium and/or in any existing vertical defect. Removal of inflamed epithelial and connective tissues on the external surface was also achieved in order to promote faster inflammation reduction. Subsequently, blood coagulation was accomplished with defocused irradiation and without the cooling water spray. Irradiation was accomplished using the tip parallel to the root surfaces, starting at the deepest portion of the periodontal pocket, in a sweeping motion, slowly moving towards the coronal aspect of the pocket.

Inclusion criteria:

- Signed and dated Informed Consent
- Good general health
- Participants ≥ 18 years of age
- Participants with ≥ 20 teeth with 5 teeth, including at least 1 molar, in each quadrant of the mouth
- Participants with $\geq 30\%$ of the present teeth with Probing depths of > 4mm and BoP
- Non-smoker and former smokers (stopped smoking > 1 year)
- Participants that have not received any periodontal treatment in the past 3 months

Exclusion criteria:

- Participants with uncontrolled systemic diseases that could affect the treatment outcome such
 as Diabetes with HbA1c > 7.0 percent, rheumatoid arthritis, immunosuppression, HIV with
 detectable viral loads
- Participants requiring antibiotic prophylaxis for any cardiovascular conditions or after any transplant and/or replacement procedures
- Pregnancy
- Patients treated with systemic antibiotic therapy of periodontal/mechanical/local delivery therapy within 6 weeks prior to study entry and throughout the study duration
- Patients being chronically (two weeks or more) treated with any NSAIDs, steroids or any medications known to affect soft tissue condition (excluding treatment with Acetylsalicylic acid < 100 mg/day)
- Presence of orthodontic appliances, or any removable appliances that impinges on the tissues being assessed
- Presence of soft or hard tissue tumors of the oral cavity
- The presence of any medical or psychiatric condition or any other condition that, in the opinion of the Investigator, could affect the successful participation of the patient in the study

RECRUITMENT

All patients seen in the pre-doctoral and post-doctoral clinics at Columbia University College of Dental Medicine were considered as potential subjects, and all students, residents and faculty were informed of this study. If any patient met the inclusion/exclusion criteria and showed interest, the study provider was contacted to provide the patient with more information.

STUDY PROCEDURES

Microsoft ® Excel software was used to generate the random sequence that allocated right and left sides (including upper and lower quadrant on each side) to the treatment modalities. Randomization was kept in an encrypted computer to which only the provider had access to. Allocation was revealed only to provider immediately prior to the first treatment appointment.

Examiner was blinded with respect to which one of the two therapies was rendered during the entire duration of the study.

VISITS:

- 1ST VISIT: Review electronic health records, including medical history, medications and dental x rays, check inclusion and exclusion criteria, solve any questions the patient may have and obtain informed consent. The following clinical parameters were recorded: clinical attachment level (CAL), pocket depths (PD), bleeding on probing (BoP) and plaque index (PI), all of them recorded in 6 sites per tooth, and tooth mobility. Patient was given oral hygiene instructions.
 - 2ND VISIT*: Review electronic health records, including medical history, medications. Oral inspection. Treatment of the assigned side, both upper and lower quadrants, after randomization, with conventional scaling and root planing. Patient will be given oral hygiene instructions. Anesthesia: Inferior alveolar blocks for the mandible and local infiltration for the maxilla with Lidocaine 2% 1:100,000 epinephrine for healthy patients Carbocaine 3% no epinephrine for patients with cardiovascular issues.
- 3RD VISIT*: Review electronic health records, including medical history, medications. Oral inspection. Treatment of the assigned side, both upper and lower quadrants, after randomization, with Er:YAG laser therapy. Patient will be given oral hygiene instructions. Anesthesia: Inferior alveolar blocks for the mandible and local infiltration for the maxilla with Lidocaine 2% 1:100,000 epinephrine for healthy patients Carbocaine 3% no epinephrine for patients with cardiovascular issues.
- 4TH VISIT, 1 month follow up. Review electronic health records, including medical history, medications. Patient was given oral hygiene instructions.
- 5TH VISIT, 3 months follow up. Review electronic health records, including medical history, medications. The following clinical parameters were recorded: CAL, PD, BoP and PI, all of them recorded in 6 sites per tooth, and tooth mobility. Periodontal maintenance with Cavitron ® and hand instruments (11/12 and 13/14 gracey's, 11/12 and 13/14 mini gracey's, 4R/4L curette and sickle scaler) was performed. Patient was given oral hygiene instructions.
- * 2^{ND} and 3^{RD} appointments were given within 10 days of each other in order to complete non-surgical periodontal treatment of the whole mouth within that period of time.

INFORMED CONSENT PROCESS

Informed consent with written documentation was obtained from the research participant, by study provider. Due to the high number of Hispanic patients that were expected to be recruited, informed consent in English and Spanish was created and approved by Columbia University's Rascal.

OBJECTIVES

The primary objective of the present study was to compare periodontal clinical parameters (CAL, PD, BoP and PI) after non-surgical periodontal therapy completed with the afore mentioned treatment modalities.

Secondary objectives included record the differences in duration of treatment between the 2 arms of the study, assessing the differences in sensitivity, and evaluate subjects' modality of preference.

POTENTIAL RISKS AND BENEFITS

Therapy for periodontal disease could involve slight soreness and sensitivity, manageable with any *over-the-counter* analgesic. Soft gingival tissues could experience shrinkage due to resolution of inflammation, situation in which clinical crowns of the treated teeth could appear to be slightly longer than previous to the therapy performed.

There is no direct benefit for participating in the study; participants will be contributing to research for treating periodontal disease. However, after treatment, gingival inflammation, sensitivity, soreness, spontaneous or induced bleeding and halitosis will improve after periodontal therapy. Once the etiology of periodontal disease, bacteria, is removed, we hope to arrest the disease progression with the provided active therapy and the subsequent recall visits.

The alternative is not to participate in the study. However periodontal disease should, in all cases, be treated. The alternatives patients would have, are either to refuse all proposed treatments or to undergo therapy with only conventional hand instruments.

STATISTICAL PROCEDURES

Wilcoxon signed-rank test will be performed to assess the significance of the results pertaining to CAL and PPD (significance level of 5%). Student's t test to analyze BOP scores (significance level of 5%) SAS 9.2

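### The planned tests ignore which side was allocated to laser: valid on average over simple randomisation, but any consistent right-left difference costs power and, in an uneven list, enters the laser-SRP contrast

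*Combined protocol and SAP*

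**What the plan says.** STUDY DESIGN states: "The study was conducted as a randomized, split-mouth clinical trial", and "Thirty subjects were recruited". The unit allocated is a whole side of the mouth. The second-visit entry under VISITS confirms this: "Treatment of the assigned side, both upper and lower quadrants, after randomization, with conventional scaling and root planing". The third-visit entry says the same for laser. Only two assignments are therefore possible per patient: laser right with SRP left, or laser left with SRP right.

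On how the assignment was drawn, STUDY PROCEDURES says only that Excel "software was used to generate the random sequence that allocated right and left sides". It describes no blocking and no requirement that the two assignments occur equally often.

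STATISTICAL PROCEDURES is two sentences long. The first is that a "Wilcoxon signed-rank test will be performed to assess the significance of the results pertaining to CAL and PPD" at the 5% level; the second names a Student's t test for BOP at the same level. Neither includes a term or stratum for side or allocation group. The section does not state whether the t test is paired, or whether the unit is a site, a tooth or a side.

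**The concern.** Side plays the part here that period plays in a two-period crossover. A patient's laser-minus-SRP difference is the treatment effect plus the right-left difference if laser was on the right, and the treatment effect minus it if laser was on the left. A test that pools these differences treats a systematic right-left effect as random scatter. With at most 30 within-patient contrasts, avoidable scatter is expensive. If one assignment happens to be more frequent, the right-left effect no longer cancels, and part of it is reported as a difference between laser and SRP, in a direction set by chance. Adjusting for first-visit values would remove only asymmetry already present at that visit, not asymmetry arising during treatment, home care or healing.

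**Working it through.** **Inputs.** From the documents: 30 patients, two possible assignments per patient, 5% significance level. Assumed, because the documents are silent: two-sided testing, one value per side per patient, a paired analysis, a true effect of 0.55 SD, and a range for the right-left difference. The plan contains no power or sample-size figure to reproduce.

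**Model.** D = τ + sδ + e, where D is laser minus SRP, s = +1 if laser is on the right and -1 if on the left, δ is the right-minus-left difference, SD(e) = σ, and d = δ/σ. Let p be the share of patients with laser on the right. If s is ignored:

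- mean of D = τ + (2p-1)δ
- variance of D = σ² + 4p(1-p)δ², which is σ²(1+d²) at p = 1/2.

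**Lost power.** Without a side term the noncentrality is 0.55·√30/√(1+d²), with 29 df. With a side term at 15:15 it is 0.55·√30 = 3.01, with 28 df, whatever d is.

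| d | variance factor 1+d² | paired-t power, no side term | with side term, 15:15 |
|---|---|---|---|
| 0 | 1.00 | 82.9% | 82.8% |
| 0.1 | 1.01 | 82.6% | 82.8% |
| 0.3 | 1.09 | 79.6% | 82.8% |
| 0.5 | 1.25 | 74.0% | 82.8% |

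In patients, the loss is 30 - 30/1.09 = 2.5 at d=0.3 and 30 - 30/1.25 = 6.0 at d=0.5. With a side term on an unrestricted list, averaged over the binomial split, power is 81.5%. The no-side-term column is closest to an average over unrestricted lists. Simulation with an effect of 0.53 SD and d=0.5 gave 70.4% on such lists and 72.7% on a fixed 15:15 list, so the loss is slightly smaller when the list is balanced.

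**Leak in an uneven list.** The fraction of δ entering the estimate is 2p-1: (18-12)/30 = 0.20 at 18:12 and (20-10)/30 = 1/3 at 20:10. For Binomial(30, 0.5), P(18:12 or worse) = 36%, P(20:10 or worse) = 9.9% and P(exactly 15:15) = 14%.

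**Type I error of the paired t test (simulation).**

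- Averaged over unrestricted lists: 4.9% to 5.2%, with zero bias.
- Fixed 15:15, d=0.5: 2.7%, so conservative. Balancing the list without changing the analysis does not recover the power.
- Realised 20:10: about 7% at d=0.3 and 10% at d=0.5.

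**Coding of the side term.** With side coded -1/+1, the intercept is the average of the two group means of D, its standard error is (σ/2)·√(1/n_R + 1/n_L), and type I error holds at 5%. If side is centred at its sample mean, the intercept is the raw mean of D. The leak then stays while the standard error shrinks, and at d=0.5 type I error is 7.7% over unrestricted lists and 14.2% at 20:10.

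**Rank version.** The right-minus-left difference is sD. It is centred at δ+τ in the laser-right group and at δ-τ in the laser-left group. The shift between groups is 2τ, so half of it is the treatment effect and δ cancels. Simulated power on an unrestricted list, rank-sum against the planned signed-rank: 78.5% v 81.1% at d=0, 79.3% v 81.5% at 0.1, 78.9% v 79.6% at 0.2, 79.4% v 78.4% at 0.3.

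**The case against.** A reader might infer that the planned tests have an inflated false-positive rate, or that the laser-SRP comparison is biased. The documents support neither. Over simple randomisation the estimate is unbiased and type I error is about 5%. The chance leak (2p-1)δ has variance δ²/30, which is the same amount by which ignoring side widens the squared standard error, so on average the plan's own interval already covers it. The lost power and the leak should not be added together as two separate harms. In a balanced list there is no leak, only conservatism. The realised split is not reported, so leakage is a risk and not a demonstrated bias. All of this stands, and it limits the point to efficiency and to protection against an unlucky list.

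The size is also wholly assumed. The documents give no right-left difference, effect size or SD, and nothing in them shows that any of the parameters differs by side. Only a difference consistent in direction across patients counts; asymmetry that varies from patient to patient is ordinary noise that a side term cannot remove. At d=0.1 the loss is negligible. For CAL and PPD on an unrestricted list, the alternative loses power until d is between about 0.2 and 0.3.

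Finally, the statistical section leaves pairing and unit of analysis unstated, and those must be settled before a side term means anything. That also stands. What remains is that the trial will be analysed on one realised list, and that the two groups needed for protection have already been randomised and need no new data.

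**Conclusion.** The point holds as a modest, inexpensive improvement, not as a fault that invalidates the planned tests. The plan creates two allocation groups and does not use them. The consequence runs from nothing (d=0) through 3.3 points of power (d=0.3: 82.9 - 79.6) to 8.9 points (d=0.5: 82.9 - 74.0). Conditional on an uneven list, a fraction 2p-1 of the right-left difference enters the contrast. These figures rest on 30 complete pairs, one value per side, two-sided 5% testing, an assumed 0.55 SD effect and an assumed range for d. The case is stronger for BOP, where the linear adjustment is nearly free, than for CAL and PPD, where the rank-sum version pays only if d exceeds roughly 0.2 to 0.3.

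A side term does not address visit order. VISITS lists SRP at the second visit and laser at the third, so order goes with treatment and not with side; that is a separate matter.

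**What to change.** In STATISTICAL PROCEDURES, state that each patient contributes one value per side for each parameter, and that the analysis is by the two allocation groups:

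1. **BOP:** regress the within-patient laser-minus-SRP difference on side coded exactly -1/+1, not centred at its sample mean. The intercept, with 28 df, is the treatment effect.
2. **CAL and PPD:** form each patient's right-minus-left difference and compare the laser-right and laser-left groups by Wilcoxon rank-sum. Report half the Hodges-Lehmann shift as the laser-minus-SRP effect.
3. **Report the realised split** between laser-right and laser-left patients.
4. **Only if the list has not yet been drawn,** generate it as one random permutation of 15 laser-right and 15 laser-left. STUDY PROCEDURES describes the list in the past tense, so this step probably no longer applies; steps 1 to 3 do not depend on it.

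The cost is a few sentences of text, with no new data and no more patients. If there is no right-left difference, the power given up is about 0.1 point (linear model, 15:15), about 1.4 points (linear model, unrestricted list), or about 2 to 3 points (rank-sum version).

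### The planned tests for CAL, PD and BoP leave out the baseline difference between sides, although it is charted; adjusting would remove chance imbalance, usually sharpen the estimate, and guard against selection by side

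*Combined protocol and SAP*

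**What the plan says.** **Analysis.** STATISTICAL PROCEDURES states: "Wilcoxon signed-rank test will be performed to assess the significance of the results pertaining to CAL and PPD". It adds a Student's t test for BOP. Both are at the 5% level and neither has a baseline term. The section does not say which quantity enters the tests. The study purpose speaks of changes at 3 months, but the statistics section does not repeat this.

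**Data.** Under VISITS, CAL, PD and BoP are recorded at six sites per tooth at visit 1 and again at visit 5. On sample size, STUDY DESIGN says: "Thirty subjects were recruited". Each subject contributes one side to each treatment.

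**Allocation.** STUDY PROCEDURES says: "Randomization was kept in an encrypted computer to which only the provider had access to". It continues: "Allocation was revealed only to provider immediately prior to the first treatment appointment". RECRUITMENT says: "If any patient met the inclusion/exclusion criteria and showed interest, the study provider was contacted to provide the patient with more information". Visit 1 is to "check inclusion and exclusion criteria, solve any questions the patient may have and obtain informed consent". INFORMED CONSENT PROCESS adds: "Informed consent with written documentation was obtained from the research participant, by study provider". One exclusion covers conditions that, "in the opinion of the Investigator, could affect the successful participation of the patient in the study". No other person is described as holding or releasing the assignment.

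**The concern.** A split-mouth design removes differences between patients, but the two sides of one mouth can still differ in severity at baseline. Over 30 random assignments these differences average to zero only in expectation. In a given trial the laser side may start deeper or shallower. The direction of the resulting error depends on what is tested: a deeper laser side tends to show more reduction but a worse final depth. With no baseline term and the tested quantity left open, the reader can neither see the imbalance nor tell which way it pushes the result.

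A secondary reason concerns enrolment. If the one person who could open the list also took part in enrolling patients, a baseline difference by assigned side could in principle arise by selection as well as by chance. Examiner blinding protects measurement but does not act on enrolment. Since every patient receives both treatments, such selection could work only through which side is worse, not through which patients are sicker.

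**Working it through.** **Inputs.** From the documents: 30 pairs, a 5% level, and measurement at visits 1 and 5. The documents give no SD, correlation or power calculation, so there is no planned figure to reproduce. Assumed: normal side differences with equal SD (set to 1) at baseline and 3 months; correlation ρ between them of 0.3, 0.5 or 0.7; two-sided tests. Let X be the laser-minus-SRP difference at baseline and Y the same at 3 months, one value per patient.

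**1. One adjusted answer for both outcomes.** If Y = a + bX + error, then Y − X = a + (b − 1)X + error. The intercept a is the same either way. With X uncentred, a is the treatment effect when the two sides start equal. Testing 3-month values alone fixes b at 0 and testing changes alone fixes it at 1; the regression estimates it.

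**2. Chance imbalance.** The SE of the mean of X is 1/√30 = 0.183 SD, so 95% of trials fall within ±1.96 × 0.183 = ±0.36 SD. Given an imbalance d, the expected error is ρd for 3-month values and −(1 − ρ)d for changes. For d = 0.183 and ρ = 0.5 these are +0.09 and −0.09 SD, equal in size and opposite in sign.

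**3. Precision of the mean side difference.**
- 3-month values: 1/√30.
- Changes: √(2(1 − ρ))/√30.
- Adjusted: √(1 − ρ²)/√30 × √(28/27). The last factor is the average price of estimating the slope from 30 pairs.

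| ρ | 3-month values | Changes | Adjusted |
|---|---|---|---|
| 0.3 | 0.183 | 0.216 | 0.177 |
| 0.5 | 0.183 | 0.183 | 0.161 |
| 0.7 | 0.183 | 0.141 | 0.133 |

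At ρ = 0.5 the variance ratio is 0.75 × 28/27 = 0.78, so 30 adjusted pairs do the work of about 30/0.78 = 38 unadjusted ones. Adjustment beats 3-month values when ρ² > 1/28 (ρ above about 0.19). It beats changes when 1 + ρ < 2 × 27/28 (ρ below about 0.93).

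**4. Selection by side, as illustration only.** Suppose patients whose laser side looks less favourable are enrolled with relative probability q. Reaching 30 then means turning away 30 × 2/(1 + q) − 30 patients: 1.6, 5.3 or 10 for q = 0.9, 0.7 or 0.5.

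With no treatment effect, and an impression of the side difference that correlates 0.7 with charted severity, Wilcoxon rejection on 3-month values at ρ = 0.3, 0.5, 0.7 was (100,000 simulated trials per cell):
- q = 0.9: 5.2%, 5.1%, 5.1%
- q = 0.7: 5.1%, 5.7%, 6.5%
- q = 0.5: 5.9%, 7.7%, 10.6%

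With perfect knowledge of the side difference (4,000 trials per cell, so a true 5% shows as about 4.3% to 5.7%), the ranges over ρ were:

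| q | Wilcoxon, 3-month values | Wilcoxon, changes | Regression intercept |
|---|---|---|---|
| 0.75 | 5.3–6.8% | 6.0–6.3% | 4.9–5.5% |
| 0.5 | 7.0–17.6% | 8.3–13.2% | 4.6–5.4% |
| 0.25 | 11.8–48.8% | 16.1–33.7% | 4.4–4.5% |

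With no selection all three analyses gave 4.4–5.6%.

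The regression holds its level here because these settings let selection act only through charted severity. If the impression also has a partial correlation of 0.2 to 0.3 with the outcome beyond charting, then at q = 0.5 the regression rejects in 5.4–6.6% of trials, against 7.3–15.4% for Wilcoxon (impression correlation 0.5 to 0.7).

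**The case against.** A reader might infer from the provider's sole access that concealment failed and that the comparison is biased. The documents do not support that. The assignment was to be revealed just before the first treatment appointment, which places it after consent and charting at visit 1. Patients had already met the criteria and shown interest before the provider was contacted. The text does not say who repeats the eligibility check at visit 1, or that the Investigator whose opinion counts for one exclusion is the provider. That the provider and the study provider are one role is a natural reading, but it is not stated. That no independent holder is named may be only a gap in a short protocol. All of this stands. What remains is that nothing described enforces the timing beyond the provider's own restraint.

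A reader might also take the rejection rate of about 18% at q = 0.5 as a worst case. It is not: it depends on the selection strength assumed, and the rate nears 49% at q = 0.25. Equally, it is no estimate for this trial.

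It can also be said that testing changes already uses the baseline. That is partly so, but changes over-correct whenever the slope is below 1, and the statistics section does not commit to them.

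Finally, with sides assigned at random, the unadjusted tests are valid without a baseline term. This is correct, and it is why the point concerns precision and chance imbalance first.

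**Conclusion.** The point holds and is minor. The planned tests omit a baseline difference that is already charted, and leave the tested quantity unstated. Adjustment lowers the SE from 0.18 to about 0.16 SD at ρ = 0.5 (about 12%). At ρ = 0.3 the gain over 3-month values is negligible, and at ρ = 0.7 the gain over changes is small (0.14 to 0.13). These figures rest on assumed correlations, normality and equal SDs at the two times. The case does not need any selection to have occurred. Provider control of the list adds a secondary reason: selection by side is possible, the documents show no sign of it, its size cannot be derived from them, and mild selection would hardly matter.

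**What to change.** Add to STATISTICAL PROCEDURES wording to this effect: *For each of CAL, PD and BoP, one value per side is computed for each patient. The laser-minus-SRP difference in 3-month change is regressed on the uncentred laser-minus-SRP baseline difference of the same measure. The intercept, with its 95% CI, is reported as the treatment effect at equal baseline, beside the planned test. Baseline values are tabulated by assigned side.*

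Say also whether the planned tests use changes or 3-month values. The past tense of STUDY DESIGN suggests that recruitment is complete, so the regression should be labelled as added at that stage.

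The cost is three regressions of 30 rows and one table, from data already collected at visits 1 and 5, with 28 residual degrees of freedom instead of 29. The adjustment corrects only for charted severity, not for anything the charting misses.

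### Only the side of the mouth is randomised; scaling and root planing always comes first and laser second, so treatment cannot be separated from order

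*Combined protocol and SAP*

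**What the plan says.** All references are to the combined protocol and SAP.

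- **Study Procedures.** Excel generated a "random sequence that allocated right and left sides (including upper and lower quadrant on each side) to the treatment modalities". Order of treatment is not mentioned, here or under Study Design. "Allocation was revealed only to provider immediately prior to the first treatment appointment", which fits side-only randomisation, because the provider must know which side to treat first.
- **Visits.** The 2nd visit is "Treatment of the assigned side, both upper and lower quadrants, after randomization, with conventional scaling and root planing". The 3rd visit is "Treatment of the assigned side, both upper and lower quadrants, after randomization, with Er:YAG laser therapy". The footnote says that these "appointments were given within 10 days of each other". There is one baseline recording (1st visit) and one outcome recording for both sides ("5TH VISIT, 3 months follow up"). The date from which the 3 months are counted is not stated.
- **Objectives.** "Secondary objectives included record the differences in duration of treatment between the 2 arms of the study, assessing the differences in sensitivity", and patients' preferred modality.
- **Statistical Procedures.** "Wilcoxon signed-rank test will be performed to assess the significance of the results pertaining to CAL and PPD", with Student's t test for BoP, both at 5%. No order or period term is planned.

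**The concern.** Randomising the side protects against left/right differences. It does nothing about differences between a first and a second treatment session. If every patient has scaling and root planing first, any such difference is added to the laser-versus-conventional difference.

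Several differences between the sessions follow from the schedule. The laser side has healed for less time at the common examination. The laser session comes after one more round of hygiene instruction and when the opposite side is already debrided. The first could work against laser and the other two for it, so the net direction for CAL, PD, BoP and PI is unknown.

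Duration and preference compare the two sessions directly. A shorter or preferred laser session could reflect the modality, or simply that it was the second visit. The same ambiguity applies to sensitivity, although the plan does not say when sensitivity is assessed. Examiner blinding does not help, because the asymmetry lies in how treatment is delivered.

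**Working it through.** The plan gives no power calculation, SD or effect size, so there is no stated figure to reproduce. The check has three parts.

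**1. Can treatment be separated from order?** Inputs: 30 patients (Study Design), two sides each, visit content as in Visits. Let the second-minus-first session effect be b and the true laser-minus-conventional effect be τ. The side difference in patient i is

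d_i = τ + b + e_i

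for every patient. Only the sum τ + b can be estimated. The rank of the design matrix (60 rows) shows the same:

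| Terms | Columns | Rank |
|---|---|---|
| Fixed order: patient + treatment | 31 | 31 |
| Fixed order: + session order | 32 | 31 |
| Fixed order: + order + healing days, constant gap | 33 | 31 |
| Fixed order: + order + healing days, varying gap | 33 | 32 |
| Balanced order: all terms, varying gap | 33 | 33 |

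A gap that varies between patients makes a healing-time slope estimable, but the order effect stays aliased with treatment. Under fixed order, treatment and order correlate at 1.00, while treatment and side correlate at 0 with sides balanced.

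**2. Healing time.** Take 3 months as 90 days and the gap at its 10-day ceiling.

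- Clock from visit 2: conventional side 90 days, laser side 80; 10/90 = 11%.
- Clock from visit 3: conventional side 100 days, laser side 90; 10/100 = 10%.

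**3. Illustration of the effect on error rate.** Assumptions, none from the documents: all 30 patients analysed, normal side differences, τ = 0, a two-sided test (the plan does not state sidedness), and the listed b and SD of the side differences. For a paired t test the rejection rate comes from the noncentral t distribution with 29 df and ncp = b√30/SD. For example, b = 0.10 and SD = 0.4 give ncp = 0.10 × 5.477/0.4 = 1.37 and a rate of 26.3%. The Wilcoxon signed-rank rates come from 100,000 simulations with the exact critical value (W ≤ 137, size 4.97%).

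False-positive rate, Wilcoxon / paired t:

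| SD (mm) | b = 0.05 mm | b = 0.10 mm | b = 0.20 mm |
|---|---|---|---|
| 0.3 | 13.9 / 14.3% | 41.0 / 42.3% | 93.3 / 94.2% |
| 0.4 | 9.7 / 10.2% | 25.2 / 26.3% | 73.5 / 75.4% |
| 0.6 | 7.1 / 7.3% | 13.7 / 14.3% | 40.9 / 42.3% |
| 0.8 | 6.2 / 6.3% | 9.9 / 10.2% | 25.4 / 26.3% |

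At b = 0.02 mm the paired t rate is 5.2 to 6.4% over the same SDs. The paired t column is an analytic cross-check; the plan does not assign a t test to CAL or PPD.

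**With order balanced 15/15**, b enters with opposite signs in the two halves and cancels from the mean. Left unmodelled, it only adds spread. Over the same grid the false-positive rate is 1.8 to 4.9% (Wilcoxon) and 1.9 to 4.9% (t), and 4.9 to 5.0% for a linear model with an order term.

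**The case against.** - **The visit list may be shorthand.** It follows the same sequence as the two modalities listed under Study Design, and order may have varied in practice. No text says so, however. The point is therefore about the schedule as written; if practice differed, the schedule needs correcting.
- **Ten days is little against a 3-month endpoint.** This stands for healing time. The largest table entry needs an order effect two-thirds of the SD (0.20/0.3), for which there is no source. The table should not set the weight of the point.
- **The table is in millimetres, so it does not address duration, sensitivity or preference.** This is correct, and no test is planned for those outcomes. The argument there is structural: a difference cannot be attributed. Calling them the most exposed is a judgement, particularly for sensitivity, whose timing is unstated. The aliasing applies whenever they are assessed.
- **Hygiene instruction starts at visit 1, before either treatment.** True: both sides share the calendar exposure, and only its timing relative to treatment differs. This makes it a weak mechanism.
- **Treatment is probably complete.** Much of the text is in the past tense. In that case only the reporting remedy is available.
- **The benefit of balance assumes near-balance among analysed patients.** With a 20/10 split, a bias of b × (20 − 10)/30 = b/3 remains. At SD 0.3 mm and b = 0.20 mm the unmodelled Wilcoxon rate was 12.6%. An 18/12 split gave about 5%, so only marked imbalance matters.

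None of this restores the ability to separate treatment from order.

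**Conclusion.** The concern holds. As written, treatment and session order are completely aliased, and this cannot be repaired in the analysis. That conclusion needs no numerical assumption.

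The size of the resulting bias is not known. The only bound in the documents is the healing gap of at most 10 days. For the 3-month clinical measures the effect may be small and its direction is open: on the illustrative inputs, the false-positive rate runs from close to 5% to above 90%, depending on the assumed order effect and SD. For duration, sensitivity and preference, a difference between modalities cannot be told apart from a difference between first and second sessions.

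It should be fixed because the remedy is cheap, not because a large bias has been shown.

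**What to change.** **If treatment is not complete.** Add a column to the existing Excel list that randomises, balanced 15/15, which modality is given at the first treatment visit, and reword visits 2 and 3 to match. The content of each treatment session and the number and spacing of visits stay the same. The planned tests can stay. Check that the order split among analysed patients remains close to even. An order-stratified or regression analysis of the side differences is an optional refinement; it would replace the Wilcoxon test, which takes no covariate.

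Cost: one column and a wording change, with no extra visits, patients or staff. If order matters and is not modelled, some power is lost. With an assumed true effect of 0.25 mm, Wilcoxon power falls by at most about 5 points over the grid, for example from 89.7% to 84.5% at SD 0.4 mm and an order effect of 0.20 mm. A linear model with an order term gives 90.9% in that case, for one degree of freedom.

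**If treatment is complete.** State whether order was fixed. If it was, report each patient's gap between visits 2 and 3, state where the 3-month clock starts, describe the comparison as conventional first versus laser second, and limit conclusions on duration, sensitivity and preference. If order varied, correct the visit schedule and report the order actually used. The cost is reporting only.
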